5.4 Quality of Life Analysis

Both between and within group analyses will be performed. Between group analyses will compare the QOL scores recorded from the EFFORTLESS S-ICD cohort with the MIDAS cohort of transvenous patients using a mixed model approach with repeated measures. Within group analyses will examine determinants of poor Quality of Life within the S-ICD cohort. All analyses will be performed using both a univariable and multivariable approach. Multivariable analysis provides the potential to adjust for factors that may impinge on the relationship between the independent variable and the dependent variable (endpoint).

5.5 Additional Data Analysis

- Conversion efficacies for both induced and spontaneous episodes and first shock will be summarized as the number of subjects and the percentages relative to the Registry population including the corresponding 95.0% two-sided exact binomial confidence interval.
- Clinical event rates will be presented as 30-day event rates as summarized by number of subjects and its corresponding percentage and 95.0% two-sided exact binomial confidence interval and long-term rates as either linear rates or Kaplan-Meier freedom from event.
- Linearised rate of inappropriate therapies will also be calculated by dividing the total number of inappropriate therapies by the total number of follow-up patient years. Linearised rate calculation will only be initiated if a minimum of 100 patient years have been reached.
- Kaplan-Meier estimates and curves for therapy delivered including:
 - Time to first therapy delivered (both appropriate and inappropriate)
 - Time to first appropriate therapy delivered
 - Time to first inappropriate therapy delivered
- Re-occurrence of inappropriate shock therapy after reprogramming will be calculated using the total number of additional inappropriate shocks recorded from patients who have previously experienced at least one inappropriate shock and had their S-ICD reprogrammed in an attempt to resolve the issue (adjustments may include but are not limited to, changing sensing vector, adjustment to ECG gain, reprogramming of shock rates)
- Considering that patients who are prospectively enrolled in this Registry will come from the investigator's general ICD population, it is a priori unknown how many will be primary versus secondary prevention patients. Analyses will be conducted for primary versus secondary prevention, for inclusion in separate cost-effectiveness models for those populations.

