3.2.1 Observational Data Collection

When available, descriptive statistics will be used to present observational data to further characterize the performance of the S-ICD system. This can include (but is not limited to):

- Clinical Indications for implant
- Patient demographics
- Type of anesthesia/analgesia
 - General anesthesia/local anesthesia/conscious sedation etc.
- Implant procedure duration
- Use of fluoroscopy and X-Ray
- Induced Shock Conversion Efficacy
 - Defined as any shock delivered by the S-ICD pulse generator that terminates the induced arrhythmia and does not require an external defibrillator.
- Spontaneous Shock Conversion Efficacy
 - Defined as any shock delivered by the S-ICD pulse generator that terminates the spontaneous arrhythmia (device defined end of episode)
- First Shock Conversion Efficacy
 - Defined as the percentage of successful conversions (device defined end of episode) caused by the first shock delivered by the S-ICD pulse generator. Data will be evaluated for both induced and spontaneous episodes
- All cause therapy (appropriate and inappropriate)
 - Inappropriate therapy is defined as delivery of shock therapy for any rhythm other than VT/VF.
- Total Shock Burden
 - Defined as the total number of therapies delivered (both appropriate and inappropriate) divided by the total number implanted patients
- Complication rates over time
- Frequency of scheduled and unscheduled follow-ups/hospitalizations
- All cause mortality
- Length of hospital stay
 - Where possible, hospital stay lengths will be calculated for implant procedure as well as scheduled and unscheduled follow-ups

- All clinical events
- Clinical event rates over time
- QOL Assessments
 - Patients will complete a brief set of standardized QOL questionnaires at baseline (pre-implant), 3 months post-implant, 6 months post-implant and 12-months post implant (see section 7.8) with the intention of comparing scores with a transvenous ICD cohort
- Hospital personnel implant and Follow-Up Experience (using an optional survey to be completed at two time points)

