7.3.2 Acute Defibrillation Testing

After implanting the S-ICD System, a ventricular arrhythmia can be induced using the S-ICD pulse generator, a temporary endocardial pacing catheter, or an alternative induction method at the discretion of the investigator. If conversion testing is performed during the initial implant procedure (or at any subsequent follow-up-scheduled or unscheduled) the following definitions will be applied to the testing with respect to data collected on the case report form:

- A *successful conversion* is defined as any shock delivered by the S-ICD pulse generator that terminates the induced VT/VF arrhythmia (device declared end of episode) and does not require an external defibrillator. This includes episodes where VT/VF converts but an atrial tachyarrhythmia may persist.
- A *failed conversion* is defined as the need for an external defibrillator following the inability of the S-ICD pulse generator to convert the VT/VF arrhythmia.
- An *attempt* is defined as an induction resulting in VT/VF that does not receive therapy (most probably due to the rhythm breaking prior to delivery of shock) and/or an induction not resulting in VT/VF.

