- Scan for devices, resulting in a display of pick list of S-ICD devices
- Establishment and termination of communication link
- Display of a real-time S-ECG
- Selection of programmable parameters
- Review of patient event history

S-ICD System Sensing and Detection

Prior to the commencement of sensing and detection of normal sinus rhythm (NSR) and/or arrhythmic events, Sensing Setup must be performed. This setup procedure may begin once the S-ICD pulse generator and subcutaneous electrode are implanted and connected.

The S-ICD System incorporates three possible sensing vectors: (1) Primary; (2) Secondary; and (3) Alternate. A Vector Selection algorithm is designed to automatically select the best sensing vector from the available vector choices. The algorithm measures critical components of the S-ECG signal and determines the best vector through analysis of signals recorded through these components. A Sense Vector Optimization algorithm is designed to incorporate the effect of posture into the vector selection algorithm.

The optimization is skipped during the implant procedure when positioning the patient in multiple postures is not practical. However, when utilized post-implant, the optimization algorithm will evaluate changes in sensing qualities that result from patient posture changes. A Reference ECG Acquisition (Template Formation) algorithm is designed to store the morphology of the patient's ECG during normal sinus rhythm. This template is later used while the S-ICD System continuously monitors the subcutaneous ECG for any tachyarrhythmia events.

Defibrillation Therapy

Once a defibrillation shock is deemed necessary, the pulse generator charges and up to 5 maximum energy (80 J) shocks are delivered for each episode. The defibrillation waveform is a truncated exponential, 50% tilt, biphasic waveform delivered between the pulse generator and the subcutaneous electrode coil. With the exception of shocks delivered manually or during induction testing, shock energy level is non-programmable and set to the maximum (80 J) output. The S-ICD System attempts to deliver all shocks synchronously with a detected cardiac event. An Adaptive Shock Polarity algorithm is designed to automatically select the polarity for the first shock delivered, based on the polarity of the last delivered successful shock. The algorithm will automatically alternate shock polarity for any necessary subsequent shocks.

Post-Shock Pacing

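### Conversion efficacy is defined per shock or episode (3.2.1) but reported per subject with an exact binomial interval (5.5), and patients with mixed outcomes have no scoring rule

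*Combined protocol and SAP*

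**What the plan says.** Section 3.2.1 defines three measures, none of them for a subject.

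- Induced conversion: "Defined as any shock delivered by the S-ICD pulse generator that terminates the induced arrhythmia and does not require an external defibrillator".
- Spontaneous conversion: "Defined as any shock delivered by the S-ICD pulse generator that terminates the spontaneous arrhythmia", with the device declaring the end of the episode.
- First-shock conversion: "Defined as the percentage of successful conversions (device defined end of episode) caused by the first shock". This counts conversions, for induced and spontaneous episodes alike.

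Section 5.5 gives all three one treatment: "Conversion efficacies for both induced and spontaneous episodes and first shock will be summarized as the number of subjects and the percentages". The percentages are taken over the Registry population, with a "95.0% two-sided exact binomial confidence interval".

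Repeats within a patient are expected. Section 7.3.2 allows conversion testing at implant "or at any subsequent follow-up-scheduled or unscheduled". Appendix E, Table 8 allows it again at a system replacement or revision. Spontaneous episodes accrue over 60 months (section 4.3). Section 7.3.2 defines a successful and a failed conversion for each test, so one patient can have both.

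**The concern.** The definitions and the analysis use different units, and no rule links them. A patient whose first episode converted and whose second did not could be a success, a failure, or one of each, depending on a choice the plan does not make. That choice could then be made after the data are seen.

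Elsewhere the plan does settle the unit. Endpoint 3 in section 5.3 counts a patient with at least one inappropriate shock. The linearised rate in 5.5 counts therapies over patient-years. Section 5.4 uses a repeated-measures model for quality of life. Conversion efficacy has neither a subject rule nor a method for repeated outcomes.

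The three Registry endpoints cover complications and inappropriate shocks, so conversion efficacy is the planned description of whether shocks terminate the arrhythmia. A favourable scoring rule would raise it most in patients with recurrent arrhythmia. Pooling episodes could make the interval too narrow.

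**Working it through.** **Inputs from the documents.** The definitions and interval method above; up to 5 shocks per episode (Appendix A, Defibrillation Therapy); 60 months of follow-up.

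**Inputs assumed.** The documents give no conversion rate, number of episodes per patient or intraclass correlation (ICC). I take 100 patients with episodes, per-episode conversion p = 0.90 (then 0.95 and 0.98), and ICC 0.1 to 0.3.

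**Step 1: the plan's exact interval.** No precision is stated for conversion efficacy. The nearest figure is Table 1 in section 5.6, which uses the same method for the 30-day endpoint.

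- 90 of 100: exact limits 82.4% and 95.1%, so -7.6/+5.1, as printed.
- 810 of 900: 87.9% and 91.9%, so -2.1/+1.9, as printed.
- All 90 cells reproduce to rounding (largest difference 0.05 points).

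The method is therefore sound when each subject gives one outcome.

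**Step 2: effect of the scoring rule, two episodes per patient.**

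- P(at least one converts) = 1 - [(1-p)² + ICC·p(1-p)]
- P(both convert) = p² + ICC·p(1-p)

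With p = 0.90 and ICC 0.3, ICC·p(1-p) = 0.3 × 0.09 = 0.027.

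- Any: 1 - (0.010 + 0.027) = 96.3%
- All: 0.810 + 0.027 = 83.7%

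With p = 0.98 and ICC 0.3, the term is 0.3 × 0.0196 = 0.00588.

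- Any: 1 - (0.0004 + 0.00588) = 99.4%
- All: 0.9604 + 0.00588 = 96.6%

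**Step 3: a more realistic spread of episodes.** Simulation, 4,000 runs per setting: episodes per patient are 1 plus a negative binomial count (mean 2.0 or 2.5, coefficient of variation about 0.76 to 0.95), and patient-level conversion probability is Beta. Many patients then have one episode, so the inflation is smaller than in Step 2.

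| Per-episode rate | Any episode converted | All episodes converted |
|---|---|---|
| 90% | about 94% (93.5% to 94.7%) | 81% to 85% |
| 95% | about 97% | about 90% to 92% |
| 98% | about 99% | about 96% to 97% |

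At 90%, 8% to 14% of treated patients have mixed outcomes. They are the group without a rule.

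**Step 4: effect of pooling episodes.** With m episodes per patient the variance is multiplied by 1 + (m-1)·ICC. Taking p = 0.90 and 100 patients:

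| m | ICC | Variance factor | Naive 95% interval | Adjusted interval | Coverage of naive |
|---|---|---|---|---|---|
| 2 | 0.1 | 1.1 | 85.0 to 93.8 | 84.7 to 94.0 | 95.7% |
| 2 | 0.3 | 1.3 | 85.0 to 93.8 | 84.1 to 94.3 | 93.8% |
| 3 | 0.1 | 1.2 | 86.0 to 93.2 | 85.6 to 93.4 | 94.9% |
| 3 | 0.3 | 1.6 | 86.0 to 93.2 | 84.8 to 93.9 | 90.7% |

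With the variable episode counts of Step 3, coverage runs from about 95% down to 84% to 86%, and the true standard error is about 1.1 to 1.5 times the binomial one. With strong skew (90 patients with 1 episode, 10 with 15, so 240 episodes), the factor is 1 + (2340/240 - 1)·ICC. At ICC 0.1 that is 1.88 and coverage is 86.8%; at ICC 0.3 it is 3.62 and coverage is 71.9%.

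**The case against.** A reader might infer from the words *any shock* in 3.2.1 that one conversion makes the patient a success over the whole follow-up. The documents do not support that as the plain meaning. The definition speaks of one arrhythmia and one episode end, the device can give up to 5 shocks in an episode, and first-shock efficacy is defined separately beside it. *Any shock* most naturally means any shock within that episode. A best-of-several count across episodes is left open by silence and is not prescribed.

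A reader might also infer that the stated interval is too narrow. As written, 5.5 counts subjects, and an exact binomial interval on one outcome per subject is valid once that outcome is defined. It is too narrow only if episodes are pooled and outcomes within a patient are positively correlated. At ICC 0.1 with two or three episodes each, the conservatism of the exact method nearly absorbs the loss. Appendix A says that first-shock polarity is chosen "based on the polarity of the last delivered successful shock". That gives a reason to expect dependence, but not its size.

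The illustrations also depend on the assumed rate. With up to 5 shocks per episode, a rate above 90% is quite plausible, and the inflation then shrinks. They divide by treated patients, whereas 5.5 refers to the Registry population; that denominator is a separate question. Larger inflation can be obtained by treating a patient's episodes as independent, but that contradicts the reason for doubting the pooled interval.

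Finally, section 5.0 calls the analyses descriptive, 3.2.1 lists these measures as observational data, and no test or sample size rests on them. All of this stands and limits the weight of the point. It does not supply the missing rule or reconcile the two sections.

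**Conclusion.** The mismatch between 3.2.1 and 5.5 is real, and it is a conflict of units as well as missing detail. With 90% conversion per episode and the other assumed inputs, the same data could be reported as about 94% or as 81% to 85%, depending on an unstated rule. A pooled per-episode interval would cover from about 95% down to 84% to 86%. At 98% conversion the any-conversion rule overstates by only about 1 point. None of these inputs is in the documents, so the sizes are illustrative. The point should be corrected, in proportion to its place as a descriptive secondary measure.

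**What to change.** In section 5.5, state the unit for each measure.

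- **Spontaneous conversion, first shock and final shock:** use the treated VT/VF episode as the unit, with a 95% interval clustered by patient (patient-level bootstrap, or GEE with robust variance). Also report the share of treated patients in whom every episode converted.
- **Induced conversion:** keep the exact binomial interval, on one prespecified outcome per tested patient, for example the first induced VT/VF test at implant where available. List later tests separately.

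One sentence defining a subject-level rule would be the minimum repair. The fuller change is preferable because it matches the definitions in 3.2.1 and uses all treated episodes.

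The cost is SAP wording and minor programming, slightly wider intervals and possibly a lower headline percentage. Spontaneous episodes are already requested from implant onwards (Table 3). Induced tests will be incomplete: testing is optional, Table 5 data are requested if available, and the minimal dataset for retrospective enrolments in section 5.9 does not name induced tests. The number of patients tested should therefore be reported beside the induced rate.

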5.0 Statistical Methods and Analysis

The statistical analyses related to this Registry including the Sub-Study (see Appendix E) will be executed by the Boston Scientific Clinical Department and/or consultants working on behalf of Boston Scientific. All patients enrolled in the Registry will be included in the analysis. As an observational non-randomized single arm evaluation, the statistical analyses will be descriptive.

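### Section 5.5 divides conversion efficacy by the whole Registry population, so patients never tested or never treated count as not converted, and its unit differs from the first-shock definition in 3.2.1

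*Combined protocol and SAP*

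**What the plan says.** Section 5.5 covers three measures of conversion efficacy in one sentence: "induced and spontaneous episodes and first shock will be summarized as the number of subjects and the percentages relative to the Registry population", each with a two-sided 95% exact binomial interval. 'Registry population' is not defined. Section 5.0 points to everyone enrolled: "All patients enrolled in the Registry will be included in the analysis".

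Section 3.2.1 describes first-shock efficacy differently: "Defined as the percentage of successful conversions (device defined end of episode) caused by the first shock delivered by the S-ICD pulse generator". It adds: "Data will be evaluated for both induced and spontaneous episodes".

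Testing is not required. Section 7.3.2 gives definitions that apply "If conversion testing is performed during the initial implant procedure" or at a later follow-up, and Table 3 marks both defibrillation testing and induced episodes as collected only if done. Section 7.3.2 also has a category, the 'attempt', for inductions that yield no VT/VF or no therapy. The minimal dataset for retrospective patients in 5.9 covers treated spontaneous episodes but does not list induction results. Section 8.1 allows for patients who are withdrawn before any implant procedure begins.

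**The concern.** A conversion can succeed or fail only in a patient who had a ventricular arrhythmia for the device to convert. The 5.5 denominator includes patients for whom this never happened: those not tested, those with no treated spontaneous VT/VF episode and, if the population is everyone enrolled, those never implanted. None of them can enter the numerator, so the calculation treats them as not converted.

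The result would move with how often patients are tested or have episodes, and not only with how well shocks work. Comparisons would suffer too. Section 5.5 plans analyses of primary versus secondary prevention patients, and if these groups differ in episode frequency, their percentages would differ even with equal shock performance.

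The unit is a second problem. Subjects over the Registry population (5.5) and conversions or episodes (3.2.1) cannot give the same first-shock percentage, and the plan does not say which to report. Nor does it say when a patient with several episodes counts as converted.

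**Working it through.** **Inputs from the documents.** Population about 1000 (synopsis, Sample Size); two-sided 95% exact binomial interval (5.5); numerator in subjects, denominator the Registry population (5.5).

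**Inputs assumed.** The documents give neither the share of patients tested or treated (f) nor the conversion rate (e). I take e = 98%, one episode per patient, f = 5% to 50% for spontaneous episodes and f = 60% to 90% for induced testing.

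**Check of the interval method.** The plan states no conversion-efficacy figure to reproduce, but Table 1 in 5.6 uses the same exact interval. For 90% at n = 900 (810/900) the limits are 87.85% and 91.88%, that is -2.1/+1.9, as printed. All 180 limits in Table 1 reproduce to the printed decimal.

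**Formula.** Converted patients = N × f × e. Dividing by N gives f × e, which cannot exceed f. Dividing by the N × f evaluable patients gives e.

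| Measure, f | As 5.5 reads (95% CI) | Evaluable patients only (95% CI) |
|---|---|---|
| Spontaneous, 5% | 49/1000 = 4.9% (3.6 to 6.4) | 49/50 = 98.0% (89.4 to 99.9) |
| Spontaneous, 10% | 98/1000 = 9.8% (8.0 to 11.8) | 98/100 = 98.0% (93.0 to 99.8) |
| Spontaneous, 50% | 490/1000 = 49.0% (45.9 to 52.1) | 490/500 = 98.0% (96.4 to 99.0) |
| Induced, 60% | 588/1000 = 58.8% (55.7 to 61.9) | 588/600 = 98.0% (96.5 to 99.0) |
| Induced, 90% | 882/1000 = 88.2% (86.0 to 90.1) | 882/900 = 98.0% (96.9 to 98.8) |

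The two columns agree only when every patient is evaluable. In none of these rows does the 5.5 interval contain 98%.

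**Ordering.** A group with f = 20% and e = 80% scores 0.20 × 0.80 = 16.0%. A group with f = 10% and e = 98% scores 0.10 × 0.98 = 9.8%. The group with the poorer conversion rate looks better.

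**First shock.** Assume 100 treated VT/VF episodes in 100 patients, 88 of them ended by shock 1. Section 5.5 gives 88/1000 = 8.8% (7.1 to 10.7). Per episode with a first shock, the result is 88/100 = 88.0% (80.0 to 93.6).

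**Repeated episodes.** A per-episode interval that assumes independence is too narrow when patients contribute several episodes. With an assumed 2 episodes per patient and within-patient correlation ρ, the design effect is 1 + (2 - 1)ρ. For ρ = 0.1 to 0.5 this is 1.1 to 1.5, and the interval widens by its square root, 1.05 to 1.22 times.

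**The case against.** The strongest reply is that this is loose drafting. The same denominator phrase is used for Endpoint 1 in 5.3 and may have been carried over. Section 3.2.1 limits observational statistics to what is available, 5.7 promises the number of data behind each variable, and 5.5 plans a Kaplan-Meier curve for "Time to first appropriate therapy delivered". A sensible analyst would probably not publish 9.8% as a conversion efficacy. That may be so, but none of these provisions changes the stated percentage or interval. If the analyst departs from the text, the unit, the denominator and the handling of attempts are chosen after the data are seen. The plan can name a narrower group when it means one: Endpoint 3 is divided by implanted patients.

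It is also fair that little hangs on these figures. They are not among the three Registry Endpoints, section 5.0 calls the analyses descriptive, and the precision tables in 5.6 cover only Endpoints 1 and 2.

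Three stronger readings that a reader might infer are not supported:

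- That 3.2.1 drops unconverted episodes from the first-shock denominator. With 98 of the 100 episodes above converted, that reading gives 88/98 = 89.8%. But the definition can equally mean the percentage of episodes converted by shock 1. Only the difference in unit from 5.5 is certain.
- That 5.5 itself uses an at-risk denominator for recurrent inappropriate shocks. That item counts shocks "recorded from patients who have previously experienced at least one inappropriate shock" and had the device reprogrammed, but it states no denominator, so it is not a useful contrast.
- That 7.3.2 seriously misclassifies inductions. A failed conversion "is defined as the need for an external defibrillator following the inability of the S-ICD pulse generator to convert the VT/VF arrhythmia", so an induced VT/VF that gets no S-ICD shock and is then externally defibrillated could fit both that category and 'attempt'. The case is remote, since the text expects most attempts to be rhythms that stop before the shock, and it is separate from the denominator.

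**Conclusion.** The point holds. As written, 5.5 yields the evaluable share times the efficacy for all three measures, with an interval for that product, and no other section narrows the denominator. The first-shock measure is also specified in two units that cannot agree. The arithmetic is exact, but the size is illustrative: it depends on an assumed N of 1000, 98% conversion and one episode per patient. On those assumptions the distortion is very large for spontaneous episodes (4.9% to 49.0% reported instead of 98.0%) and smaller but still material for induced tests (58.8% to 88.2%).

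A reader might infer that the Registry will publish misleadingly low efficacy, or that its endpoints are affected. The documents support neither: the tested and treated shares are not given, and the Registry Endpoints are defined separately. This is a plan that should be corrected, not one whose main results are in doubt.

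**What to change.** In 5.5, replace the Registry population for these measures with two stated groups, reported separately:

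- patients with at least one evaluable induced VT/VF episode, leaving out the 7.3.2 attempts;
- patients with at least one treated spontaneous VT/VF episode.

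Keep the exact binomial interval for these per-patient figures and state the success rule for a patient with several episodes (for example, converted in every evaluable episode).

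Define first-shock efficacy in the same words in 5.5 and 3.2.1: VT/VF episodes ended by shock 1, divided by VT/VF episodes that received a first shock, with induced and spontaneous episodes reported separately. The VT/VF restriction is needed because Appendix A counts an episode as treated once any shock is delivered, so shocks for AF or SVT would otherwise enter. Use an interval that allows for repeated episodes within a patient, and state the numbers of patients and episodes in each denominator.

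Two additions are optional: saying which 7.3.2 category prevails where both fit, and listing known VT/VF episodes with no delivered shock. The first could mean revisiting completed case report forms.

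The core change costs some wording in 5.5 and 3.2.1 and a little analysis of data already requested. Two limits should be stated with the results: episode data are requested only if available, and sections 7.4.1 and 7.5.1 send copies of printouts to the sponsor only when linked to endpoint data, which conversion efficacy is not.
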